Note: This document is signed electronically through submission and approval by the Principal Investigator in the University of Utah IRB Electronic Research Integrity and Compliance Administration (ERICA) system.

STUDY SUMMARY

Title	The Use of Low-Dose Carvedilol to Improve Hypoglycemia Awareness in Patients with T1DM
Short Title	Carvedilol for Hypoglycemia Unawareness
Protocol Number	IRB #: 00108879
IND	Exemption Approved
Phase	Phase II
Design	Double-blinded, randomized, placebo-controlled study.
Study Duration	From Fall 2018 to Spring 2020
Study Center(s)	University of Utah Health
Objectives	The aim of the study is to investigate whether low-dose carvedilol treatment can improve hypoglycemia awareness and the counterregulatory hormone responses to hypoglycemia in Type 1 diabetic patients with impaired awareness of hypoglycemia.
Number of Subjects	A total of 21 Type 1 diabetic patients with impaired awareness of hypoglycemia will be recruited for the study – 7 subjects will be treated with placebo and 7 subjects will be treated with one of two different doses of carvedilol (2.5 or 3.125mg).
Diagnosis and Main Eligibility Criteria	
Patients with Type 1 diabetes and hypoglycemia unawareness will be included in this study.
 
Inclusion criteria:
 
 • Type 1 diabetes of >5yrs duration • >18yrs of age • Impaired hypoglycemia awareness/unawareness assessed by validated questionnaires. • Intensive insulin treatment as defined by multiple daily insulin injections (3 or more) or insulin pump therapy. • Negative pregnancy test. • Signed informed consent. 
Exclusion Criteria:
 
 • Major medical disorders (including liver disease, cardiovascular disease, kidney disease, COPD, asthma, active malignancy and HIV).

	
 • Overt diabetic complications (neuropathy, nephropathy, retinopathy). • Anemia. • Current or recent use of beta-blocker therapy. • Use of diuretics. • Allergies or contraindications to beta-blockers or heparin. • Pregnant. • Use of benzodiazepines. • Alcohol, drug or medication abuse. • Frequent use of acetaminophen.
Study Product, Dose, Route, Regimen	Hypoglycemia unaware T1DM subjects will be randomly segregated into one of two therapeutic treatment groups: Placebo or Carvedilol. Carvedilol will be administered orally at either 2.5mg or 3.125mg twice daily. Likewise, the placebo drug will also be administered orally twice daily.
Duration of Administration	4 weeks
Reference Therapy	Placebo
Statistical Methodology	Treatment effects will be analyzed using one- or two-way analysis of variance (ANOVA) for independent or repeated measures as appropriate, followed by suitable post-hoc analysis. Analyses will be performed using the GraphPad Prism® or SAS® suite of software.

STUDY SCHEMA

[figure not shown]

Figure 1: Schematic of the study design.

1. OBJECTIVES

1.1 Primary Objectives and Endpoints

- To investigate whether T1DM patients with impaired awareness of hypoglycemia receiving carvedilol treatment will show marked improvements in hypoglycemia symptomatic awareness scores, as well as improvements in their counterregulatory hormone responses to hypoglycemia.

1.2 Secondary Objectives and Endpoints

- To investigate whether carvedilol treatment reduces the amount of time T1DM patients with hypoglycemia unawareness spend in the hypoglycemic range as assessed by blinded CGM.
- To investigate whether carvedilol reduces the fear of hypoglycemia.

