9.11.2 Secondary Objective Assessment

The secondary objective assessment will establish whether the frequency of CGM-determined hypoglycemic episodes differs during 4 weeks of carvedilol treatment compared to baseline and compared to the placebo-treated control group.

Patients will wear a blinded CGM that is installed 14 days prior the first clamp study and the device will continue to be worn throughout the entire study. These CGMs will be calibrated using the provided Bayer Contour Next EZ[®] glucometer. During the first clamp study, the follow-up visit and the second clamp study, data from the CGM will be downloaded and saved onto a secure server and exported into an Excel format for analysis. We will identify the number hypoglycemic excursions during the intervention period and compare this to the number of hypoglycemic episodes encountered during the 7-day period before the first clamp study, the “baseline” period. Comparisons between treatment groups at baseline and following the intervention period, as well as differences from baseline within each treatment group will be made.

Analysis of the CGM data will emphasize the number of hypoglycemic episodes as well as the duration and depth of the hypoglycemic episodes. A single hypoglycemic episode is defined as a glucose reading <70 mg/dL, followed by a reading ≥ 70 mg/dL, lasting at least 15 minutes or at least two readings below 70mg/dL over 15 minutes. If there is less than 30 minutes between two registered episodes of hypoglycemia these are considered as one episode.

We will also evaluate the answers to the fear surveys to determine whether those patients who are treated with carvedilol have a reduction in their fear of hypoglycemia compared to those on placebo.

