10 STATISTICAL CONSIDERATIONS

A total of 21 T1DM patients with impaired awareness of hypoglycemia will be sought for this study. For the dose response study, we plan to enroll 21 of these patients who will be randomized to either placebo (N=7) or carvedilol (2.5mg or 3.125mg twice daily; N=7 each).

In estimating the appropriate sample sizes required to yield adequate statistical power, assuming a Type II error rate (β) of no more than 20% for a given test and a Type I error rate of $\alpha=5\%$, we used the following: $\text{Power} \geq 1-\beta = 1-0.2 = 0.8$

Treatment effects will be analyzed using one- or two-way analysis of variance (ANOVA) for independent or repeated measures as appropriate, followed by suitable *post-hoc* analysis. Analyses will be performed using the GraphPad Prism[®] or SAS[®] suite of software. We will use a significance level of $\alpha<0.05$.

Primary variables:

- a) Symptom Scores (autonomous, neuroglycopenic and other symptoms of hypoglycemia)
- b) Counterregulatory Hormone Responses (glucagon, epinephrine, norepinephrine, growth hormone and cortisol levels)

Secondary variables:

- a) Frequency of hypoglycemia assessed by CGM.

The primary and secondary variables will be analyzed by the statistical approaches mentioned above.

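### The CGM secondary objective is time spent in hypoglycemia, but the listed variable is episode frequency, and time below 70 mg/dL is never defined or given a test

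*Combined protocol and SAP*

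**What the plan says.** Section 1.2 gives two secondary objectives. The CGM one is whether carvedilol treatment "reduces the amount of time T1DM patients with hypoglycemia unawareness spend in the hypoglycemic range", measured by blinded CGM. The other is "To investigate whether carvedilol reduces the fear of hypoglycemia".

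Section 9.11.2 sets the secondary assessment as "whether the frequency of CGM-determined hypoglycemic episodes differs during 4 weeks of carvedilol treatment", against baseline and against placebo. It defines an episode, gives a rule for merging neighbouring episodes, and compares the number of episodes in the intervention period with the number in a 7-day baseline. It then adds: "Analysis of the CGM data will emphasize the number of hypoglycemic episodes as well as the duration and depth of the hypoglycemic episodes." It also says that the fear surveys will be evaluated.

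Section 10 has a single entry under secondary variables: "Frequency of hypoglycemia assessed by CGM". It closes with: "The primary and secondary variables will be analyzed by the statistical approaches mentioned above." Those approaches are one- or two-way ANOVA with post-hoc analysis.

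**The concern.** The objective and the listed variable are different quantities. Time below range depends on how many lows occur and on how long each lasts, while frequency captures only the first.

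The distinction matters for this intervention. Section 9.10 says symptoms generally first appear at 55-65 mg/dL in people who are aware, while the episode definition in 9.11.2 starts below 70 mg/dL. Restored awareness would therefore tend to act after an episode has already begun. Section 2 describes symptoms as the trigger for eating, and glucagon and epinephrine as raising glucose again. Both routes shorten a low more directly than they prevent one.

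At stake is whether the secondary result answers the question in 1.2. There is also some freedom to choose the headline: 9.11.2 names number, duration and depth, Section 10 names only frequency, and 1.2 names none of these.

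**Working it through.** **Figures in the plan.** The plan gives no figure for this point that could be reproduced. The sample size of 21 (7 per arm) comes with alpha 5% and power of at least 80% but no effect size or SD, and the point does not depend on it.

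**The sections side by side**

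| Measure | 1.2 | 9.11.2 | 10 |
|---|---|---|---|
| Time in hypoglycemic range | objective | not defined | not listed |
| Episode frequency | not mentioned | assessment, compared between periods and groups | only secondary variable |
| Episode duration, depth | not mentioned | to be emphasized; no summary or test stated | not listed |
| Fear of hypoglycemia | objective | to be evaluated | not listed |

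**Inputs from the documents**
- Episode: below 70 mg/dL for at least 15 minutes (9.11.2; two low readings over 15 minutes also qualify).
- Merging: a gap under 30 minutes makes two episodes one (9.11.2).
- Windows: 7-day baseline (9.11.2) and 28 days of treatment (6.3).

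**Assumed inputs.** The number and length of lows are illustrative. The documents give no CGM episode rate, duration or variance.

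**Step 1: the relation.** Time below 70 = (number of episodes) x (mean minutes below 70 per episode) + minutes in lows too short to count as episodes.

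**Step 2: same count, less time.** One week is 7 x 1,440 = 10,080 minutes. With one episode a day:

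| Minutes per episode | Episodes per week | Minutes below 70 | Percent of week |
|---|---|---|---|
| 120 | 7 | 7 x 120 = 840 | 8.3% |
| 60 | 7 | 7 x 60 = 420 | 4.2% |
| 30 | 7 | 7 x 30 = 210 | 2.1% |
| 15 | 7 | 7 x 15 = 105 | 1.0% |

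From 120 to 30 minutes, frequency changes by 0% and time falls by (840 - 210)/840 = 75%. At 3 episodes a week, 3 x 90 = 270 against 3 x 45 = 135 minutes: 0% for frequency and a 50% fall in time.

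**Step 3: higher count, less time.** Replace each daily 120-minute low by two 30-minute lows that are 45 minutes apart. Each fragment passes the 15-minute rule, and the 45-minute gap is too long to merge. The count rises from 7 to 14, while time falls from 840 to 7 x 60 = 420 minutes.

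**Step 4: unequal windows.** The treatment period is 28/7 = 4 times the baseline window. At a constant one episode a day the raw counts are 7 and 28. Section 9.11.2 states no scaling to a daily rate. Percent of wear time, or a rate per day of wear, removes the difference.

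**The case against.** The strongest reply is that 9.11.2 already commits to duration and depth. Number and duration together recover nearly all the time below 70 mg/dL, so the shortening in Step 2 would be seen. This stands. A reader might infer that the trial would miss a fall in episode length, or would report no effect when time had fallen. The documents do not support that, since it would require ignoring 9.11.2. What remains is that duration per episode is not total time, leaves out lows too short to count, and has no stated summary or test.

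A second reply is that the Section 10 lists look abbreviated. They also omit the detection threshold, which is a primary assessment in 9.11.1, and the ANOVA wording covers treatment effects generally. So one cannot conclude that unlisted measures would go untested. That is fair. Even so, a measure that no section defines cannot be taken as planned.

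Third, frequency is the consistent working measure: Section 4.1 also uses it for baseline, and Section 2 argues that hypoglycemia leads to more hypoglycemia. Rewording 1.2 to frequency would restore consistency. It would do so by giving up the question that 1.2 asks, although the CGM data needed to answer it are already collected.

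Fourth, this is a secondary endpoint in a small trial. With 7 per arm, two-sided 5% and 80% power, a pairwise t-test needs a difference of about 1.63 SD, so a null result on either CGM measure would be inconclusive. This limits the weight of the point but does not settle which quantity should be analysed.

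**Conclusion.** The mismatch is real. Section 1.2 sets an objective about time, 9.11.2 and Section 10 operationalize it as frequency, and no section defines total or percent time below 70 mg/dL or gives it a test. Under the plan's own episode rules, frequency can stay flat (0%) while time falls by 50% to 75%, or double while time halves. A frequency result therefore does not answer the stated objective.

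These sizes rest on assumed durations. They show that the two measures can separate, not by how much they will in this trial. The planned look at duration and depth narrows the gap but does not close it. No stated figure in the plan changes. The same omission from Section 10 affects the other secondary objective, fear of hypoglycemia.

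**What to change.** In 9.11.2 and Section 10:

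- Name percent of valid CGM wear time below 70 mg/dL, per participant, as the secondary CGM variable for the 1.2 objective. Compute it for the 7-day baseline and for the 28-day treatment period.
- Add a short wear-time rule: what counts as valid CGM time, and how much is needed in each period for a participant to be included.
- Compare arms adjusting for the baseline value. In a three-arm model with 21 participants, one covariate takes the residual degrees of freedom from 21 - 3 = 18 to 17.
- Keep episode frequency (per day of wear), duration and depth as supportive measures.
- Add the fear survey to the Section 10 list of secondary variables.

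The cost is a wear-time definition, edits to two sections and a little extra analysis of data already downloaded. No new visits, devices or participants are needed. The documents give no mean or SD for percent time, so no power can be claimed for it. The result should be reported as an estimate with its confidence interval.

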2 BACKGROUND

Hypoglycemia elicits a multifaceted hormonal response that helps restore glycemic levels to normal. As blood glucose levels start to fall, insulin secretion ceases. At the top of this hierarchy of counterregulatory responses are glucagon and epinephrine which are the two principal hormones that act rapidly to increase glucose production and inhibit glucose utilization to raise plasma glucose levels back to normal¹. In cases of prolonged and/or more severe hypoglycemia, growth hormone and cortisol are mobilized to stimulate the synthesis of gluconeogenic enzymes and inhibit glucose utilization². In non-diabetic individuals, glucagon and epinephrine are usually very effective and the latter responses are rarely required in the acute situation. In contrast, impaired glucose counterregulation presents itself in longstanding diabetes and with antecedent hypoglycemia³. Within the first five years after the onset of Type 1 diabetes (T1DM), the primary defense against hypoglycemia, the release of glucagon, either becomes significantly attenuated or is completely absent in diabetic patients and this impairment appears to be specific for the stimulus of hypoglycemia^{4,5}. Hence, patients with diabetes primarily depend on the release of epinephrine as their main defense against hypoglycemia. Unfortunately, with longer duration of diabetes and especially with poor glycemic control, epinephrine secretion is also compromised, making these patients even more vulnerable to the threat of hypoglycemia⁵⁻⁷. In patients with diabetes, hypoglycemia arises from the interplay of a relative excess of exogenous insulin and defective glucose counterregulation and it remains a limiting factor in attaining proper glycemic management. Both the Diabetes Control and Complications Trial (DCCT) conducted in Type 1 patients⁸ and the United Kingdom Prospective Diabetes Study (UKPDS) conducted in Type 2 patients⁹, have established the importance of maintaining good glucose control over a lifetime of diabetes to avoid cardiovascular, renal and neurological complications. However, lowering glycemic goals for diabetic patients increases their risk for hypoglycemia exposure. According to the DCCT, T1DM patients put on intensive insulin therapy, though having improved outcomes for diabetic complications, are at a 3-fold higher risk of experiencing severe hypoglycemia compared to those on conventional insulin therapy¹⁰. Moreover, recent antecedent hypoglycemia reduces autonomic (epinephrine) and symptomatic (which normally

prompts behavioral defenses such as eating) responses to subsequent bouts of hypoglycemia¹¹⁻¹⁴. Thus begins the vicious cycle of recurrent hypoglycemia (RH) where hypoglycemia leads to further impairment of counterregulatory responses which in turn, begets more hypoglycemia and so forth. Because of the imperfections of current insulin therapies, those patients attempting to achieve glycemic control suffer an untold number of asymptomatic hypoglycemic episodes. Current estimates of symptomatic hypoglycemic episodes range from 2-3 incidences per week on average and severe, debilitating episodes occur once or twice each year. Therefore, developing therapies to prevent or eliminate hypoglycemia is of great importance.

Sensors that detect changes in blood glucose levels and initiate glucose counterregulatory responses have been identified in both the periphery¹⁵⁻²⁰ and within the brain²¹⁻²⁹. These sensors have been localized to the hepatic portal vein^{17,18}, the carotid body³⁰ and the brain^{21,22,24,31}. In the brain, the dominant sensors are located in the hypothalamus. While peripheral glucose sensors may play a role in mediating the immediate counterregulatory responses to hypoglycemia, it is thought that glucosensors located within the brain may have a redundant regulatory and/or modulatory role in regulating glucose counterregulatory responses. It is well established that brain glucose sensors are crucial for detecting falling blood glucose levels and for initiating counterregulatory responses^{22,31}. These sensors are located in the hindbrain, the lateral hypothalamus, the paraventricular nucleus, the dorsal hypothalamus and the ventromedial hypothalamus (VMH)^{22,27,32-34}. The neurons within the VMH contain much of the same glucose sensing machinery as the pancreatic β -cells²⁹. To date, two main types of glucose sensing neurons have been identified in the brain – those that increase their firing rate in response to increases in glucose levels, the “glucose-excited” or GE neurons and those that decrease their firing rate in response to increasing glucose levels, the “glucose-inhibited” or GI neurons³⁵⁻³⁸. The mechanism by which GE neurons sense changes in blood glucose concentrations is believed to be similar to that used by pancreatic β -cells³⁹ whereas GI neurons respond to decreases in ambient glucose levels through activation of the metabolic fuel sensor, AMP kinase (AMPK), and closure of chloride channels that result in increased activity of GI neurons^{28,40}. Although many of these sensing components have been identified, it is still not entirely clear how glucose sensing neurons regulate counterregulatory hormone release. It has been proposed that alterations in the firing rates of VMH glucose sensing neurons in response to glucose or fuel deficits can inhibit (as is the case for GE neurons) or stimulate (as is the case for GI neurons) the exocytosis of vesicles containing neurotransmitters that can modulate the counterregulatory hormone response^{39,41,42}.

The inhibitory neurotransmitter, GABA, and the stimulatory neurotransmitters, glutamate and norepinephrine, act within the VMH to suppress or stimulate the counterregulatory responses to hypoglycemia, respectively. In response to an initial bout of hypoglycemia, VMH GABA levels decrease while glutamate and norepinephrine levels increase, allowing for activation of the counterregulatory hormone responses⁴³⁻⁴⁷. While these studies underscore the importance of VMH neurotransmitter signaling in regulating glucose homeostatic mechanisms, to date, the mechanisms that lead to their dysregulation in models of counterregulatory failure are not entirely clear. Recent evidence suggests that lactate, which serves as an alternate fuel substrate in the brain, plays an important role in precipitating the defects noted above^{48,49}. Lactate produced from neighboring astrocytes can supplement higher energy requirements during periods of increased neuronal activity or when glucose supply is limited⁵⁰. If this is

the case, then lactate can be used in place of glucose as a fuel for VMH glucose sensing neurons, preventing them from detecting a fall in glucose levels, causing (inhibitory) GABA tone to be enhanced and (stimulatory) glutamate output to be reduced. Together, these actions ultimately suppress the release of counterregulatory hormones. In recent years, it has been shown that lactate levels are sensed by the brain and more specifically, can act in the hypothalamus to regulate glucose homeostasis, appetite and body weight⁵¹⁻⁵⁶. Lactate prevents the activation of hypothalamic neurons during glucose deprivation^{51,57} and more pertinent to this application, attenuates glucose counterregulatory responses to hypoglycemia when locally administered into the VMH⁵⁸. Data from our research group revealed VMH extracellular lactate concentrations are elevated in RH and diabetic animals and in particular, these conditions also increase expression of the lactate transporter, MCT2, in the VMH⁴⁸. When VMH lactate uptake is pharmacologically inhibited using 4CIN, we can improve neurotransmitter and counterregulatory responses in both RH and diabetic animals, suggesting lactate plays an important role in dysregulating neurotransmitter systems in the VMH, which in turn, impairs counterregulatory responses. *Our preliminary data suggests that therapeutic strategies that can reduce brain lactate levels, may help restore hypothalamic glucose sensing mechanisms and the counterregulatory response to hypoglycemia.* Hence, identifying the mechanisms that increase VMH lactate levels may lead to suitable therapeutic strategies to prevent hypoglycemia.

[figure not shown]
To this end, we investigated one mechanism that can enhance lactate production and/or utilization in the brain - activation of norepinephrine (NE) receptors. Norepinephrine can enhance lactate production from astrocytes and it can also increase the uptake of lactate into neurons through the activation of β 2-adrenergic receptors (β 2AR), potentially helping to co-ordinate both the supply and uptake of lactate into neurons⁵⁹⁻⁶¹. Normally, in response to an acute bout of hypoglycemia, VMH norepinephrine levels rise and act through β 2ARs to enhance the sympathoadrenal response^{46,62,63}. Although activation of VMH β 2ARs augments the counterregulatory response during *acute* bouts of hypoglycemia, less is known about the effects of RH on this neurotransmitter system. It has been reported that VMH NE levels are not altered by successive bouts of hypoglycemia, suggesting activation of the VMH NE system is not dampened by RH and that its suppressive effects on counterregulatory hormone release may lie downstream of NE release⁶⁴. In support of this finding, *adrenergic blockade during antecedent bouts of hypoglycemia was shown to prevent counterregulatory failure* in healthy human subjects⁶⁵. Therefore, while *acute* activation of VMH adrenergic receptors may be beneficial in its capacity to enhance the counterregulatory response, *repeated* activation of this neurotransmitter system may contribute to counterregulatory failure, but the mechanism(s) by which this occurs have not been fully identified.

To evaluate whether repeated activation of the VMH NE system contributes to counterregulatory failure, we locally microinjected NE into the VMH of non-diabetic, hypoglycemia-naïve rats for 3hrs/d for 3 consecutive days before subjecting the animals to a hypoglycemic glucose clamp on day 4 (Figure 1). Repeated activation of the VMH NE system in the absence of hypoglycemia, increased VMH lactate levels and more importantly, blunted the counterregulatory hormone responses to hypoglycemia. This phenomenon was recapitulated with microinjection of salbutamol, a short-acting β 2AR agonist, into the VMH using the same protocol as for NE, suggesting the suppressive effects of NE are mediated through VMH β 2ARs. In a subgroup of animals treated with NE, we administered 4CIN into the VMH to block

the uptake of lactate into neurons immediately prior to the hypoglycemic clamp. In this group, we saw the suppressive effects of NE treatment on glucose counterregulation were completely abolished. Hence, our preliminary data suggests that repeated activation of the VMH NE system plays a role in the development of counterregulatory failure, in part by enhancing central lactate production and therefore, the use of β -adrenergic blockers may be a promising treatment to preserve the responses to hypoglycemia. As proof-of-concept, our preliminary data shows that RH rats treated with low doses of the non-specific β -blocker, carvedilol (3mg/kg, *intraperitoneally*), during the induction of RH, required less exogenous glucose during the hypoglycemic clamp compared to RH animals treated with vehicle (Figure 2). More importantly, we also saw reductions in VMH lactate levels and significant improvements in the counterregulatory hormone responses to hypoglycemia in the carvedilol-treated RH animals.

It is important to note, however, that treatment of diabetic patients with β -blockers has been somewhat controversial due to its perceived potential to attenuate the responses to hypoglycemia. However, compelling clinical evidence to support this possibility is lacking. In the recent GEMINI study which evaluated the use of two different β -blockers in T2DM patients with hypertension, carvedilol, was shown to effectively reduce overall hypoglycemia burden scores⁶⁶. Likewise, the vast majority of clinical studies show that treatment of non-diabetic and T1DM patients with β -blockers improved counterregulatory hormone responses without increasing the frequency of hypoglycemia or hypoglycemia unawareness⁶⁷⁻⁷², although loss of tremulousness and reduced tachycardia were reported in some studies. One study found that treatment of T1DM hypoglycemia aware patients with propranolol reduced glycemic thresholds for adrenergic symptoms, but this deficit was offset by higher hypoglycemia symptom scores stemming from augmented diaphoresis⁷³. Other neuroglycopenic symptoms were not affected. Moreover, in a prospective study of 150 diabetic patients, 50 of whom were on β -blockers, no difference in the incidence of hypoglycemic unconsciousness was noted between those patients who were on β -blockers compared to those who were not, suggesting the use of β -blockers in T1DM patients does not increase the incidence of severe hypoglycemia⁶⁸ and may be a safe therapeutic option that can be used in conjunction with insulin. Therefore, the current application will evaluate the effectiveness of low-dose carvedilol as a treatment for restoring the counterregulatory hormone responses to hypoglycemia and improving hypoglycemia awareness in patients with Type 1 diabetes.

Figure 2: RH (black bars) raised VMH lactate and blunted the counterregulatory responses to hypoglycemia. Treatment with carvedilol reduced VMH lactate and improved the counterregulatory hormone responses (red bars). # $P < 0.0001$ vs Control. * $P < 0.05$ vs Control. ** $P < 0.02$ vs. Control.

Carvedilol is a third generation non-selective, vasodilating β -blocker, which is FDA-approved for the treatment of congestive heart failure and hypertension. Carvedilol mainly blocks β_2 - and β_1 -adrenergic receptors and some α_1 -adrenergic receptors. Due to its lipophilic nature, carvedilol readily crosses the blood-brain-barrier. As the brain is our primary target, this beneficial pharmacokinetic property of carvedilol improves CNS bioavailability, allowing lower doses to be used to deliver treatment to the brain. With lower doses, we can reduce the potential for side effects stemming from unnecessary exposure of peripheral tissues to high levels of β -adrenergic blockade. Based on data gathered by the Food and Drug Administration (FDA), in a population study of 36,044 patients who reported having side effects while taking carvedilol, only ~1% of these patients experienced hypoglycemia. As carvedilol is currently FDA-approved for clinical use, it can potentially be repurposed for use as a preventive treatment for hypoglycemia. Therefore, we are proposing to evaluate the effectiveness of low-dose carvedilol treatment for 4 weeks as a treatment for restoring the counterregulatory hormone responses to hypoglycemia and improving hypoglycemia awareness in patients with Type 1 diabetes.

